2.2.5. Pancreatic Cancer

Globally, pancreatic cancer is the seventh leading cause of cancer death with an estimated 432,242 deaths and 458,918 new cases in 2018 (Bray 2018). Despite advancements in detection and management, the 5-year survival rate stands at 9% only (Siegel 2020). An estimated 57,600 new cases of pancreatic cancer will be diagnosed in the US, with an estimated 47,050 deaths in 2020. An IHC screen of pancreatic cancer specimens revealed that 20 of 20 total specimens (100%) exhibited ADAM9 expression at any level, while 17 of 20 (85%) had H-scores > 100 (ie, moderate or strong expression) (Hicks 2019).

Evaluation of second-line therapy in randomized trials indicates that 16 to 57% of patients with pancreatic cancer receive salvage chemotherapy after failure of first-line gemcitabine (Heinemann 2012). Median OS in gemcitabine-resistant patients receiving best supportive care was 2.3 months in a small randomized trial (Heinemann 2012).

Pancreatic ductal adenocarcinoma cells overexpress ADAM9, and increased ADAM9 expression correlates with poor tumor grading and the presence of vasculature invasion (Oria 2019). Similarly, Grutzmann et al. demonstrated that ADAM9 is overexpressed in pancreatic ductal adenocarcinomas and that cytoplasmic ADAM9 expression associates with poor survival in patients who underwent curative resection of these tumors (Grutzmann 2004). Thus, ADAM9 may be a potential target for treatment of pancreatic ductal adenocarcinoma.

2.3. **IMGC936**

IMGC936 is an ADC targeted against ADAM9. IMGC936 consists of the maytansinoid DM21-C conjugated to the MGA021 antibody via a cleavable peptide linker. Maytansinoids are anti-mitotic agents that inhibit tubulin polymerization and microtubule assembly. MGA021 is a humanized, IgG1/kappa mAb that recognizes human ADAM9 antigen and is cross-reactive with cynomolgus monkey ADAM9. MGA021 is composed of 2 IgG1 heavy chains of 452 amino acids and 2 kappa light chains of 218 amino acids and has a molecular weight of 147,425 Da. The triple mutation M252Y/S254T/T256E (YTE) is incorporated into the Fc portion of IMGC936 to improve the neonatal Fc receptor (FcRn) binding at acidic pH and therefore enhance pharmacokinetic properties. In IMGC936, each antibody molecule is conjugated to approximately 2.0 molecules of DM21-C (drug to antibody ratio of ~1.5-2.2) via site specific conjugation to engineered cysteine residues at position 442 of the IgG1 heavy chains. Owing to

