5.4. Guidelines for Study Drug Discontinuation

Participants who tolerate study drug may continue to receive the study drug, as specified in the protocol, until any one of the following conditions are met:

- Progressive disease (PD) Objective progression per RECIST v1.1 or clinical progression as determined by investigator
 - Participants who experience PD by RECIST v1.1 should discontinue study drug.
 However, participants who have experienced clinical benefit may continue the treatment if agreed upon between the sponsor and the investigator
- AE requiring study drug discontinuation including, but not limited to, the following events:
 - Study drug-related ≥ Grade 3 cardiac event

- Study drug-related Grade 4 non hematologic event
- DLT during dose-escalation window (DLT period)
- Pregnancy
- Death
- Investigator decision
- LTFU
- Major protocol deviation requiring study drug discontinuation
- Participant declining further treatment
- Participant decision to withdraw consent for study
- The sponsor, investigator, or regulatory agency terminate the study

If the investigator decides that the participant should be withdrawn from the study or from dosing for any reason other than disease progression, the sponsor or its designee must be alerted in a timely manner by completing the appropriate eCRFs.

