9.9. Radiographic, CT, or MRI Assessments

Tumor assessments are performed according to the schedule in Appendix 1 and Appendix 2. Baseline tumor imaging consists of a CT/MRI scan with contrast, unless medically contraindicated, to document tumor burden. Subsequent tumor assessments on study should use the same imaging modality as that for the baseline assessment.

Tumor assessments are performed every 6 weeks (Q6W; \pm 7 days) on Schedule A and every 8 weeks (Q8W; \pm 7 days) on Schedule B while on study drug then every 12 weeks (Q12W; \pm 21 days). Tumor assessments continue until discontinuation criteria are met. Tumor assessments are performed at EOTV except if prior assessment was \leq 30 days of EOTV and results are available for RECIST v1.1 assessment.

CT or MRI scan of the brain will be performed when clinically indicated (eg, history or suspicion of brain metastases) and repeat brain scans will be performed only if the screening brain scan was positive, or as clinically indicated.

If feasible, participants who discontinue study drug for reasons other than PD (eg, toxicity) should continue to undergo tumor assessments Q12W until evidence of PD, initiation of another anticancer therapy, withdrawal of consent, LTFU, death, or end of study whichever occurs first.

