14.7.3. Time-to-Event Endpoints and Analyses

Progression-free survival will be defined as the time from the first dose date of study drug to the date of first documented progression or death from any cause, whichever occurs first. The documented progression is determined by objective assessment of disease per RECIST v1.1. For participants who are not known to be dead or progressed at the time of data cut off for PFS analysis, the PFS will be censored at the date of the last tumor assessment. Specifically, the following censoring rules will be applied to the PFS analysis.

Table 11: Censoring Rules for Primary Analysis of PFS

Situation	Date	Outcome	
No baseline tumor assessments	First dose date	Censored	
Death prior to first scheduled tumor assessment	Date of death	Progressed	
No post-baseline tumor assessments in absence of death prior to first scheduled tumor assessment	First dose date	Censored	
Documented progression	Date of progression	Progressed	
Initiation of alternative anti-cancer treatments in absence of documented progression	Date of last tumor assessment on or prior to initiation of such treatment	Censored	
Death or documented progression immediately after missing 2 or more consecutive scheduled tumor assessments	Date of last tumor assessment prior to missed assessments	Censored	

Abbreviation: PFS: progression-free survival

DoR is defined as the time from the date of initial response (CR or PR) to the date of first documented progression or death from any cause, whichever occurs first. The DoR is calculated only for the responders. For responders who are not known to be dead or progressed at the time of data cut-off for DoR analysis, the DoR will be censored at the date of the last tumor assessment. Specifically, the last 3 situations described in Table 11 will be applied. DoR analyses will be performed only if there are enough responders to render the analyses meaningful.

The Kaplan-Meier method will be applied to estimate PFS and DoR curves; their median times, and PFS rates at 6 and 12 months, respectively. The method of Brookmeyer and Crowley (3) will be used to construct 95% CIs for median time of each time-to-event endpoint. The 95% CIs for PFS rates at each time point of interest will be calculated by normal approximation after log(-log) transformation.

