Participants with a global deterioration of health status requiring discontinuation of study drug without objective evidence of disease progression at that time should be reported as 'symptomatic deterioration'. Every effort should be made to document objective progression even after discontinuation of study drug. Symptomatic deterioration is not a descriptor of an objective response: it is a reason for stopping study drug. The objective response status of such participants is to be determined by evaluation of target and non-target disease as shown in Table A-1 and Table A-2.

For equivocal findings of progression (eg, very small and uncertain new lesions; cystic changes or necrosis in existing lesions), study drug may continue until the next scheduled assessment. If at the next scheduled assessment, progression is confirmed, the date of progression should be the earlier date when progression was suspected.

^a If a CR is truly met at first time point, then any disease seen at a subsequent time point, even disease meeting PR criteria relative to baseline, makes the disease PD at that point (since disease must have reappeared after CR). Best response would depend on whether minimum duration for SD was met. However, sometimes 'CR' may be claimed when subsequent scans suggest small lesions were likely still present and in fact the participant had PR, not CR at the first time point. Under these circumstances, the original CR should be changed to PR and the best response is PR.

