#### 4.2. **Definition of Baseline**

Study Day 1 (ie, Cycle 1 Day 1) will be designated as the first day a patient receives study drug. The baseline value is defined as the last non-missing value on or before the date of first dose of study drug.

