#### 6.1.1. Progression-free survival (PFS)

Progression-free survival will be defined as the time from the first dose date of study drug to the date of first documented progression or death from any cause, whichever occurs first. The documented progression is determined by objective assessment of disease per RECIST v1.1. For participants who are not known to be dead or progressed at the time of data cut-off for PFS

analysis, the PFS will be censored at the date of the last tumor assessment. Specifically, the following censoring rules (Table 2) will be applied to the PFS analysis.

**Table 2:** Censoring rules for PFS

Situation	Date	Outcome	
No baseline tumor assessments	First dose date	Censored	
Death prior to first scheduled tumor assessment	Date of death	Event	
No post-baseline tumor assessments in absence of death prior to first scheduled tumor assessment	First dose date	Censored	
Documented progression	Date of progression	Event	
Initiation of alternative anti-cancer treatments in absence of documented progression	Date of last tumor assessment on or prior to initiation of such treatment	Censored	
Death or documented progression immediately after missing 2 or more consecutive scheduled tumor assessments (i.e, documented progression or death date - last radiological assessment date +1 ≥ 105 days)	Date of last tumor assessment prior to missed assessments	Censored	

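### The PFS censoring table gives zero follow-up to unscanned participants who die soon after the first scheduled scan, although the PFS definition counts death from any cause

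*SAP*

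**What the plan says.** Protocol 14.7.3 and SAP 6.1.1 define PFS alike: time from first dose to the "date of first documented progression or death from any cause, whichever occurs first". Progression means RECIST v1.1 progression. The sentence leading into the censoring table censors, at the last tumor assessment, only participants not known to have died or progressed by the data cut-off.

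Three of the six rows in the table (Protocol Table 11, SAP Table 2) matter here:

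- Row 2, "Death prior to first scheduled tumor assessment": an event on the date of death.
- Row 3, "No post-baseline tumor assessments in absence of death prior to first scheduled tumor assessment": censored at the first dose date.
- Row 6, death or progression straight after two or more consecutive missed assessments: censored at the last assessment before the gap. The SAP adds a 105-day threshold.

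No order of precedence is given. SAP 4.2 says that Study Day 1 "will be designated as the first day a patient receives study drug", so row 3 leaves no follow-up at all. SAP 6.2 reports the Kaplan-Meier median and the 3- and 6-month PFS rates. SAP 6.5 plans no sensitivity analysis.

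On scans after stopping drug, Protocol 5.4 lists under PD "Objective progression per RECIST v1.1 or clinical progression as determined by investigator". Protocol 9.9 says that, if feasible, "participants who discontinue study drug for reasons other than PD (eg, toxicity) should continue to undergo tumor assessments Q12W". The synopsis, the schema (1.1) and 11.1.1 carry the same limit. Section 9.15.2 and footnote m of Appendices 1 and 2 have no such limit. Sections 9.9 and 9.14 plan a scan at the end of treatment visit (EOTV) unless one from the preceding 30 days is available. Appendix 6 says of symptomatic deterioration: "Every effort should be made to document objective progression even after discontinuation of study drug".

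**The concern.** Rows 2 and 3 divide unscanned participants by one question: did death come before the first scheduled assessment? If yes, the death is an event. If no, the participant is censored at first dose, even when the date of death is known. A known death is then an event by the definition and by the lead-in, but not by the table.

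This censoring depends on outcome, because the people removed have failed early. The same person can count elsewhere. If drug was stopped because of death or clinical progression, SAP 4.11.2, 6.1.2 and 6.1.3 keep that person in the ORR denominator as a non-responder. At stake are the PFS median and landmark rates. PFS is a secondary endpoint in expansion and exploratory in escalation.

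**Working it through.** **Step 1: which row applies.** Take Schedule A. Two 21-day cycles put the first scan at Day 1 + 42 = Day 43, with a ±7-day window of Days 36 to 50. The second is due on Day 1 + 84 = Day 85, with its window opening on Day 78. Consider a participant who is never scanned after baseline.

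| Death on | Row | PFS result |
|---|---|---|
| Day 35 | 2 | event at Day 35 |
| Day 46 | 2 or 3, depending on whether the target date or the close of the window is meant | event at Day 46, or censored at Day 1 |
| Day 53 | 3 | censored at Day 1 |

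On Day 53 only one scheduled scan has been missed, so row 6 does not apply. It does not apply under the SAP's 105-day count either. Inclusion criterion 3 allows the baseline scan up to 28 days before Day 1, and 52 + 28 + 1 = 81, below 105. Rows 1, 4 and 5 concern a missing baseline scan, documented progression and new therapy, so they do not help.

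**Step 2: size by algebra.** The plan states no PFS median, event count or power, so there is no figure of its own to reproduce. Let a share f be affected, all of them dead by time t. Participants censored at time zero leave every risk set, so

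S_reported(t) = S_true(t) / (1 − f).

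With an assumed true 3-month PFS of 30% in a full cohort of 39:

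| Affected | Calculation | Reported |
|---|---|---|
| 1 | 0.30 / (1 − 1/39) | 30.8% |
| 2 | 0.30 / (1 − 2/39) | 31.6% |
| 4 | 0.30 / (1 − 4/39) | 33.4% |
| 8 | 0.30 / (1 − 8/39) | 37.7% |

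**Step 3: how much the EOTV scan helps.** A simulation (200,000 participants, 6-weekly scans) applied the table literally and compared it with counting every death. All inputs are assumptions:

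- median time to RECIST progression of 60, 90 or 150 days;
- 5%, 10% or 20% with clinical progression before Week 6;
- 0%, 50% or 90% of those having an EOTV scan that shows progression;
- a mean of 35 days from clinical progression to death.

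Rise in the 3-month rate, in percentage points, with 10% early clinical progressors:

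| Median | No EOTV scan | 50% scanned | 90% scanned |
|---|---|---|---|
| 60 days | 0.7 | 0.5 | 0.2 |
| 90 days | 1.7 | 1.0 | 0.5 |
| 150 days | 2.8 | 1.5 | 0.6 |

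Over all 27 combinations the rise runs from about 0.1 to 5 points. With 90% scanned it is below 1 point in eight of nine combinations and 1.1 in the other. The median is unchanged in 23 of 27. Where it moves it can jump a scan interval, for example 126 against 84 days (90-day median, 10%, no EOTV scan).

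**Cross-check.** In that same scenario 6.7% are censored at first dose. At 6 months the formula gives 24.7% / (1 − 0.067) = 26.5%, against 26.3% simulated. At 3 months it overshoots (48.9% / 0.933 = 52.4%, against 50.6%) because some of these deaths come later. Before Week 6 the literal curve is marginally lower (96.8% against 97.0% at Day 41), so the inflation is confined to later times.

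**The case against.** The strongest reply is that the consequence is small. PFS is descriptive and untested (SAP 4.9 and 4.10). An EOTV scan is planned, and one that shows progression makes the participant an event. Eligibility requires ECOG 0 or 1 (or the Karnofsky alternative) and a life expectancy above 12 weeks, so few should die unscanned soon after Week 6. This stands as to size. It does not remove the contradiction: the EOTV is to be held whenever possible, and those too ill to attend are the ones at issue.

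A reader might infer more than the documents support:

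- *That the rules discard the fastest failures.* Row 2 keeps every death before the first scheduled assessment as an event.
- *That clinical progressors are neither events nor scanned further.* They become events through later RECIST progression or death, unless row 3, new therapy or the missed-scan rule censors them. The EOTV scan, 9.15.2 and Appendix 6 all call for scanning. The fault is that these passages disagree with 9.9 and 11.1.1.
- *That a large bias is likely because the diseases are rapidly fatal.* The protocol does say "Median OS in gemcitabine-resistant patients receiving best supportive care was 2.3 months", but that comes from one small trial without active treatment in one of five tumor types. Section 2.2.1 gives 7 to 9 months for second-line NSCLC. An affected share of 15% or 20% has no support in the documents.

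Limiting progression to RECIST is a definition consistent across both documents. Counting clinical progression as an event is therefore an optional supportive view and does not correct an error.

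**Conclusion.** Row 3 is wrong as written. Read literally, it overrides the PFS definition and its own lead-in for unscanned participants who die after the first scheduled assessment but before two scheduled scans have been missed. The direction is upward for the later Kaplan-Meier estimates, by about 1/(1 − f).

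The size cannot be fixed from the documents, because f is not given. It is about 1 point or less at 3 months if most EOTV scans are done, and about 5 points in the worst combination tried. The simulated gaps somewhat overstate what the correction would change: they count all deaths, including those after two missed scans, which the corrected row would still censor.

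The reach is limited to PFS. Duration of response uses only the last three rows of the table. ORR, the primary expansion endpoint, and its Simon rule do not depend on this row.

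**What to change.** 1. In Protocol Table 11 and SAP Table 2, limit row 3 to participants with no post-baseline scan who are not known to have died before two consecutive scheduled assessments were missed. Count earlier deaths as events on the date of death. State whether the first scheduled assessment means its target date or the close of its window, and from which date the SAP's 105 days run when there is no post-baseline scan.
2. Optionally, add one supportive Kaplan-Meier analysis to SAP 6.5 that counts discontinuation for clinical progression as an event on that date.
3. Reconcile the off-drug scan wording. The synopsis, schema, 9.9 and 11.1.1 limit 12-weekly scans to stopping for reasons other than PD, and 5.4 puts clinical progression under PD. Section 9.15.2, footnote m and Appendix 6 have no such limit.

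The cost is wording in two documents and, if item 2 is taken up, one extra analysis run. Reported PFS may become slightly less favourable.

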1.1. Study Overview Schema

Abbreviations: FPI: first participant in; PFS: progression-free survival; QXW: every X weeks; RP2D: recommended Phase 2 dose.

Safety assessments occur from the time of initiation of administration of study drug through the End of Treatment Visit or 30 days following the last dose of study drug or until subsequent start of anticancer therapy.

Tumor assessments occur every 2 cycles during treatment (Q6W for Schedule A and Q8W for Schedule B) and Q12W if the participant has discontinued study treatment for reasons other than progressive disease.

Participants enrolled on Schedule B will receive study drug on Days 1, 8, and 15 of a 28-day cycle for the first 2 cycles. On all subsequent cycles (Cycle 3 and beyond), participants will receive study drug on Days 1 and 8 of a 28-day cycle. The 3 + 3 dose escalation will apply to the alternate schedule. The starting dose for Schedule B will be equal to or less than the fractionated total dose of the maximum tolerated dose or maximum administered dose on the original every 3 weeks schedule.

¹ Pharmacokinetics and immunogenicity will be assessed throughout the study (Appendix 4 and Appendix 5).

² Participants who discontinue before progression of disease will be followed for PFS after end of study treatment.

TABLE OF CONTENTS

TITLE PA	AGE	1
SPONSO	R SIGNATURE PAGE	2
INVESTI	IGATOR'S AGREEMENT	3
1.	SYNOPSIS	4
1.1.	Study Overview Schema	9
TABLE (OF CONTENTS	10
LIST OF	ABBREVIATIONS AND DEFINITIONS OF TERMS	17
2.	BACKGROUND INFORMATION	20
2.1.	Rationale for Study	20
2.2.	Disease Background	20
2.2.1.	Non-Squamous Non-Small Cell Lung Cancer	21
2.2.2.	Triple Negative Breast Cancer	21
2.2.3.	Colorectal Cancer	22
2.2.4.	Gastroesophageal Cancer.	22
2.2.5.	Pancreatic Cancer	23
2.3.	IMGC936	23
2.4.	IMGC936 Benefit/Risk in Humans	24
2.5.	Nonclinical Background on IMGC936	24
2.5.1.	IMGC936 Nonclinical Experience	24
2.5.1.1.	IMGC936 Pharmacology	24
2.5.1.2.	IMGC936 Pharmacokinetics and Toxicology	25
2.6.	IMGC936 Dose Selection	26
2.6.1.	Multiples of Monkey Exposure	27
3.	STUDY OBJECTIVES AND PURPOSE	28
3.1.	Dose Escalation Phase	28
3.1.1.	Primary Objective and Endpoints	28
3.1.2.	Secondary Objectives and Endpoints	28
3.1.3.	Exploratory Objectives and Endpoints	28
3.2.	Dose Expansion Phase	28
3.2.1.	Primary Objective and Endpoint	28

		29 March 2022
3.2.2.	Secondary Objectives and Endpoints	29
3.2.3.	Exploratory Objectives and Endpoints	29
4.	INVESTIGATIONAL PLAN	30

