5.1. Inclusion Criteria

- 1. Ability to provide informed consent and documentation of informed consent prior to any study-related tests or procedures that are not part of standard of care for the participant's disease. Participants must be willing and able to comply with study procedures.
- 2. Participants with histologically proven, relapsed or refractory, unresectable locally advanced or metastatic non-squamous NSCLC, TNBC, CRC, gastroesophageal cancer, or pancreatic cancer for whom no therapy with demonstrated clinical benefit is available. Participants in expansion cohorts must have received all appropriate approved therapy and fit within the prior lines of therapy restrictions listed below.

Note: Neoadjuvant/adjuvant systemic treatment are included as 1 line in prior lines of therapy, except for TNBC where they are excluded.

Note: Maintenance therapies are considered part of the prior line of therapy and will not be counted as a separate line of therapy.

- a. Non-squamous NSCLC: Participants in dose expansion phase may have been treated with up to 3 prior lines of systemic chemotherapy, with no limit on prior targeted therapy containing lines, eg, for targetable mutations.
- b. TNBC: Participants in dose expansion phase may have been treated with up to 4 prior lines of systemic therapy for metastatic disease, excluding checkpoint inhibitors and neoadjuvant/adjuvant therapies.
- c. CRC: Participants in dose expansion phase may have been treated with up to 4 prior lines of systemic therapy.
- d. Gastroesophageal cancer: Participants in dose expansion phase may have been treated with up to 4 prior lines of systemic therapy.
- e. Pancreatic cancer: Participants in dose expansion phase must have been treated with 1 to 3 prior lines of systemic therapy, with no more than 2 chemotherapy-containing lines.
- 3. Either non-measurable or measurable disease per RECIST v1.1 and documented by computed tomography (CT) and/or magnetic resonance imaging (MRI) obtained within 28 days of Cycle 1 Day 1.
 - a. Dose Escalation Phase: Participants may have non-measurable or measurable disease per RECIST v1.1.
 - b. Dose Expansion Phase: Participants must have measurable disease per RECIST v1.1.
- 4. Age \geq 18 years old.
- 5. Tumor tissue must be submitted. If archival tissue (formalin-fixed paraffin-embedded [FFPE] block or slides) is not available, participants may undergo a low-risk, medically routine procedure, if appropriate.

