- ^j To be obtained pre-infusion. Day 1 laboratory samples can be obtained up to 3 days before infusion. Chemistry and hematology results must be reviewed before study drug administration. See Appendix 3 for assessments.
- ^k Tumor markers are obtained as indicated for each specific tumor type, eg, CEA for colorectal cancer and CA19-9 for pancreatic cancer. Repeat collection on Cycle 1 Day 1 if screening collection > 7 days prior.
- ¹ Tumor assessments are Q8W (± 7 days) while participant is on study drug, then Q12W (± 21 days). Assessments continue until discontinuation criteria are met. Tumor assessments are performed at EOTV except if prior assessment was ≤ 30 days of EOTV and results are available for RECIST v1.1 assessment.
- ^m Tumor assessments will occur after participant has discontinued study drug Q12W (± 21 days) until evidence of PD, initiation of another anticancer therapy, withdrawal of consent, LTFU, death, or end of study, whichever occurs first.
- ⁿ Day 15 dose may be omitted in Cycle 2 if significant ocular events occurred in Cycle 1, at the discretion of the investigator.

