#### 6.1.4. **Duration of Response (DoR)**

DoR is defined only for patients who achieve a response (CR/PR) and will be measured from the

date of initial response to progressive disease or death, whichever occurs first.

Per the BOR definition, patients with an overall response of CR or PR must have a repeat tumor assessment performed no less than 4 weeks after the criteria for response are first met. The first date at which a CR or PR response was noted will be used to calculate DoR, not the date of the confirmatory tumor assessment.

DoR is only defined for responders (ie, patients who have a BOR of CR or PR). The censoring rule for DOR is same as that for PFS. Specifically, the last 3 situations described in Table 2 will be applied. DoR analyses will be performed only if there are enough responders to render the analyses meaningful.

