# 6.5. Additional Sensitivity Analyses

Not applicable.

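### The SAP's single 105-day gap for two or more missed scans fits only 6-weekly scanning, so on 8-weekly and 12-weekly schedules it can censor PFS and DoR events after one missed scan or none

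*SAP*

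**What the plan says.** Protocol 14.7.3, Table 11, censors PFS at the last scan before the gap in this case: "Death or documented progression immediately after missing 2 or more consecutive scheduled tumor assessments". It gives no day count. SAP 6.1.1, Table 2, repeats the row and adds, as its definition, "documented progression or death date - last radiological assessment date +1 ≥ 105 days". One figure serves everyone. SAP 6.1.4 extends it to duration of response: "The censoring rule for DOR is same as that for PFS".

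The scan interval is not the same for everyone. Protocol 1.1 states: "Tumor assessments occur every 2 cycles during treatment (Q6W for Schedule A and Q8W for Schedule B) and Q12W if the participant has discontinued" study drug without progression. The windows are ±7 days on treatment and ±21 days in 12-weekly follow-up (Protocol 9.9, Appendices 1 and 2). The baseline scan is "obtained within 28 days of Cycle 1 Day 1" (Protocol 5.1). A scan is also due at the end of treatment visit (EOTV) unless one was done in the preceding 30 days (Protocol 9.9 and 9.14).

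**The concern.** The SAP introduces the day count as the meaning of the row, so it is what will be programmed. A fixed gap can stand in for a number of missed scans only if the scans are evenly spaced at one known interval. With three intervals, the same 105 days can mean two missed scans, one, or none. Events that the row's own words would count then become censorings dated back to the last scan, and for some deaths the reverse happens.

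PFS is secondary in expansion and exploratory in escalation. DoR is secondary in both phases. SAP 6.5, "Additional Sensitivity Analyses", is marked not applicable, so no planned analysis would show how many events the count reclassifies.

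**Working it through.** **Where 105 comes from.** The SAP gives no derivation. Schedule A inputs reproduce it in two ways: 2.5 × 42 = 105, and 2 × (42 + 7) + 7 = 105. The same formulas give 140 and 133 for 8-weekly scanning (56 days, ±7), and 210 and 231 for 12-weekly scanning (84 days, ±21).

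**Progression found at the next regularly scheduled scan attended.** With m scans missed, interval I, and d1 and d2 the deviations of the two attended scans from their due dates:

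score = (m + 1) × I + (d2 − d1) + 1; censored if score ≥ 105.

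All window combinations are enumerated (15 × 15 = 225 for ±7; 43 × 43 = 1,849 for ±21).

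| Scanning | Missed | Score (days) | Combinations censored |
|---|---|---|---|
| 6-weekly (A) | 1 | 71–99 | 0 of 225 |
| 6-weekly (A) | 2 | 113–141 | 225 of 225 |
| 8-weekly (B) | 0 | 43–71 | 0 of 225 |
| 8-weekly (B) | 1 | 99–127 (nominal 113) | 204 of 225 (91%) |
| 8-weekly (B) | 2 | 155–183 | 225 of 225 |
| 12-weekly | 0 | 43–127 (nominal 85) | 276 of 1,849 (15%) |
| 12-weekly | 1 | 127–211 | 1,849 of 1,849 |
| 12-weekly | 2 | 211–295 | 1,849 of 1,849 |

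If each scan is instead dated from the last actual one, only d2 varies. The 12-weekly no-miss score is then 64–106, and 2 of 43 dates (about 5%) are censored. The 8-weekly one-miss score is 106–120, always censored.

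**Last scan is the baseline scan**, L = 0 to 28 days before the first dose: score = (m + 1) × I + d2 + L + 1, with 29 × 15 = 435 combinations. After one miss:
- Schedule A: 78–120, 135 of 435 censored (31%).
- Schedule B: 106–148, all 435 censored.

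The row dates this censoring to the baseline scan, on or before the first dose, where PFS time starts.

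**Deaths.** Score = days since last scan + 1, so the count is reached from day 104. The last scan is taken to be on its due date. The answer depends on when a scan counts as missed.

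| Case | Missed once due date passes | Missed once window closes |
|---|---|---|
| 8-weekly, one miss, wrongly censored | days 57–112: 104–112, 9 of 56 (16%) | days 64–119: 104–119, 16 of 56 (29%) |
| 12-weekly, one miss, wrongly censored | days 85–168: 104–168, 65 of 84 (77%) | days 106–189: all 84 (100%) |
| 6-weekly, two misses, wrongly kept as events | days 85–126: 85–103, 19 of 42 (45%) | days 92–133: 92–103, 12 of 42 (29%) |

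**The case against.** A reader might infer that on Schedule B one missed scan is nearly always enough to censor. The documents do not support that for the row as a whole. It also covers deaths, and most Schedule B deaths after one miss stay events. Nor does it hold for every progression: one documented before the next regular scan, for example at the EOTV scan, can score under 105 and count as an event. The 91% applies to progressions found at the next regular scan and is an upper figure for all Schedule B progressions after one miss.

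A reader might also infer that PFS is biased in a known direction. That does not follow. The errors run both ways, and the working compares two censoring rules with each other, not either rule with the true time of progression.

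The affected groups may also be small. Schedule B is optional (SAP 3.2). SAP 7 names 6 mg/kg as the recommended dose, a level in the Schedule A table and not in the Schedule B table. SAP 3.5 describes only 21-day dosing. Follow-up scanning is conditional: "If feasible, participants who discontinue study drug for reasons other than PD (eg, toxicity) should continue to undergo tumor assessments Q12W". DoR is analysed only if there are enough responders.

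All of this limits the size of the point. It does not remove the mismatch: SAP 3.3 lets Cohorts A to G use either schedule, and 12-weekly follow-up and baseline gaps arise on Schedule A too.

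**Conclusion.** The 105-day count contradicts the words it is meant to define, except for progressions between on-treatment Schedule A scans, where it separates one miss from two without error. The mismatch matters mainly on Schedule B and in 12-weekly follow-up. In follow-up, even a participant who misses no scan can have a progression censored.

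The score ranges rest only on the documents' intervals and windows. The shares treat all in-window dates, and all possible days of death, as equally likely, and cycle delays are not modelled. The documents do not say how many participants will be on Schedule B or in follow-up, so the number of reclassified events cannot be given. The net effect on the descriptive PFS and DoR results is probably small. The primary ORR is unaffected, and SAP 4.9 and 4.10 plan no hypothesis test. The point should still be corrected before analysis, because the rule decides which events are censored and the correction is cheap.

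**What to change.** In SAP Table 2, delete the single 105-day count. Count consecutive scheduled scans, under the schedule in force, whose window closed with no scan before the progression or death.

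If a day count is kept, use it only for progressions between scans on one interval:
- 6-weekly: 105 (between 99 and 113).
- 8-weekly: 140 (between 127 and 155).
- 12-weekly: 211. One and two misses touch at 211, so 1 of 1,849 one-miss combinations is misclassified.

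Count missed scans for deaths, for gaps from the baseline scan, and for gaps that span the change to 12-weekly scanning. For that change, state the date from which the 12 weeks run, taking the EOTV scan into account. Censor baseline gaps at the first dose date, as the table already does when there is no post-baseline scan. Apply the same rule to DoR.

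The cost is SAP wording and programming, including mapping each scan to the schedule in force. Protocol Table 11 needs no change.
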